### **6.1.3. Adjustments for Covariates**

In general, when a repeated measures analysis is used, the model will include the fixed categorical effect of treatment, pooled investigative site, visit, treatment-by-visit interaction, and the continuous, fixed covariates of the baseline value of the variable being analyzed and baseline value of the variable being analyzed-by-visit interaction. The baseline value of the variable being analyzed and the baseline value of the variable being analyzed-by-visit interaction are included to account for the differing influence over time of the baseline score on the post-baseline scores.

When an analysis of covariance (ANCOVA) model is used to analyze a continuous variable, the model will contain the main effects of treatment, pooled investigative site, and appropriate baseline values included as covariates.

Data presentations for Study Period III will be based on the same MMRM and ANCOVA models excluding treatment effect, where appropriate.

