#### 6.1.2. General Considerations

Efficacy and safety analyses will be done on an intent-to-treat (ITT) basis unless otherwise specified. An intent-to-treat analysis is an analysis of data by the groups to which patients are assigned by random allocation, even if the patient does not take the assigned treatment, does not receive the correct treatment, or otherwise does not follow the protocol.

All efficacy and safety analyses of continuous measures will include randomized patients with both a baseline and at least one post-baseline value for the variable being analyzed. For efficacy and continuous safety variables, baseline is defined as the last measurement taken at, or prior to the visit where the study period begins; endpoint is defined as the last non-missing measurement for the study period of interest. Table HMGW 6.1 provides baseline and post-baseline definitions for all variables.

Statistical analyses will be carried out for Study Period II, III, and IV (SP II-IV). All tests of hypotheses will be evaluated based on a two-sided significance level of 0.05 unless otherwise specified. No adjustments for multiple comparisons will be made.

For SP II, a patient's treatment group will be determined by the treatment to which the patient is randomized: either duloxetine (DLX) or placebo (PLA).

For SP III, the following treatment groups will be determined by the randomized treatment at SP II and extension phase treatment at SP III:

PLA/DLX: patients who are randomized to placebo at SP II and who enter SP III and take duloxetine.

DLX/DLX: patients who are randomized to duloxetine at SP II and who enter SP III and take duloxetine.

No statistical comparisons will be conducted to compare the two treatment groups PLA/DLX and DLX/DLX during SP III unless otherwise noted. For continuous measures, when appropriate, within treatment testing of change from baseline for selected safety and efficacy measures will be conducted for SP III.

For SP II/III, one treatment group will be determined by the randomized treatment at SP II:

DLX: patients who are randomized to duloxetine at SPII, including patients who may have discontinued early at SPII or who enter SPIII.

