A repeated measures analysis refers to a restricted maximum likelihood (REML)-based, mixed-effects repeated measures (MMRM) analysis using all the longitudinal observations at each post-baseline visit. The model for this analysis will include the fixed categorical effect of treatment, pooled investigative site, visit, and treatment-by-visit interaction, as well as the continuous, fixed covariate of baseline value of the variable being analyzed and baseline value of the variable being analyzed-by-visit interaction. An unstructured covariance structure will be used to model the within-patient errors. And Kenward-Roger approximation (Kenward and Roger, 1997) will be used to estimate denominator degrees of freedom. If the default Newton-Raphson algorithm used by SAS PROC MIXED does not converge, then the Fisher scoring algorithm will be applied.

However, if the model with unstructured covariance structure still fails to converge, the sandwich estimator (Diggle, Liang, and Zeger, 1994; Lu and Mehrotra, 2009) will be used to estimate the standard errors of the fixed effects parameters and the model will be fitted using covariance structures in the following order until convergence is met:

heterogeneous toeplitz	type = toeph
heterogeneous autoregressive (1st order)	type = arh(1)
heterogeneous compound symmetric	type = cs(h)
toeplitz	type = toep
autoregressive (1st order)	type = ar(1)
compound symmetric	type = cs

When the sandwich estimator is used, the Kenward-Roger approximation for denominator degrees of freedom cannot be used. Instead, the denominator degrees of freedom will be partitioned into between-subject and within-subject portions (denoted by DDFM= BETWITHIN in the MODEL statement).

For repeated measures analyses of efficacy and safety variables that are not collected at each post-baseline visit, data may exist at visits where the variable was not scheduled to be collected due to early discontinuation visits. Data collected at scheduled visits and early discontinuation visits will be used in the analysis. In these situations, the data from the early discontinuation visit will be carried forward to the next regularly scheduled collection visit for the repeated measures analysis. Significance tests will be based on least-squares means (LSMean) and Type III sum-of-squares, using a two-sided  $\alpha=0.05$ . Analyses will be implemented using SAS® PROC MIXED.

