
6. Time to event variable:  a. Time to first 30% reduction in BPI average pain score  b. Time to first 50% reduction in BPI average pain score  c. Time to sustained response
	
a. For the patients with a 30% reduction at a visit in the treatment phase in SP II, time = days from the date of the visit that the earliest 30% reduction is observed to the date of the first day of SP II. The date of the first day of SP II is the randomization date.  b. For the patients with a 50% reduction at a visit in the treatment phase in SP II, time = days from the date of the visit that the earliest 50% reduction is observed to the date of the first day of SP II.  c. For the sustained responders defined above in SP II, time = the days from the date of the visit which is the earlier visit from which the sustained response is observed to the date of the first day of SP II.
	
For Variables 6.a to 6.c, the Kaplan-Meier survival curves of time to event will be calculated by treatment group for Study Period II. In the calculation, patients who do not have the event will be considered as right-censored observation. The comparison of the survival curves between treatment groups will be conducted by a log-rank test and stratified log-rank test controlling for pooled investigator.

Abbreviations: ANCOVA = analysis of covariance; BOCF = baseline observation carried forward; BPI = Brief Pain Inventory-Adolescent Version; CDI = Children's Depression Inventory; CGI-S = Clinical Global Impressions of Severity; eCRF = electronic case report form; FDI = Functional Disability Inventory; LOCF = last observation carried forward; MASC = Multidimensional Anxiety Scale for Children; PPQ = Pediatric Pain Questionnaire.

The treatment-by-investigator interaction will be tested using an ANCOVA model. When the interaction is statistically significant, the nature of the interaction will be investigated.

Descriptive statistics will be used to summarize all variables presented in HMGW.6.3 except variables 3a-b, 5(b, d, h) and 6a-c by treatment group for all ITT patients entering Study Period III. Descriptive statistics will be used to summarize variables 1a, 2a-f, and 4a-e for Study Period II/III. For continuous measures, when appropriate, within treatment testing of change from baseline will be conducted for SP III and SP II/III.

For efficacy measures, data from all visits will be listed.

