#### **6.1.14.2. Clinical Laboratory Evaluation**

The incidence rates of patients with treatment-emergent abnormal, high or low laboratory values at endpoint (LOCF) will be summarized for SP II, SP II and SP II/II, and compared between treatment groups for SP II. Listings of abnormal lab values and treatment-emergent abnormal lab values will also be presented.

A “treatment-emergent abnormal value at endpoint” is defined as a change from normal at all visits during baseline to abnormal at endpoint. A “treatment-emergent high value at endpoint” is defined as a change from a value less than or equal to the high limit at all visits during baseline to a value greater than the high limit at endpoint. A “treatment-emergent low value at endpoint” is defined as a change from a value greater than or equal to the low limit at all visits during baseline to a value less than the low limit at endpoint. High and low reference ranges for adolescent patients will be used to determine treatment emergent abnormal, high, low values. These reference ranges will be provided by a central laboratory. The same analysis will be done for “treatment-emergent abnormal value at anytime”, “treatment-emergent high value at any time”, and “treatment-emergent low value at any time”.

Treatment emergent liver function abnormalities at any time post-baseline for patients with normal ALT values (ALT <1 time upper limit normal) at last non-missing baseline will be summarized for SP II, SP III and SP II/III, and compared between treatment groups for SP II for the following categories:

ALT  $\geq$  3 times upper limit normal

ALT  $\geq$  5 times upper limit normal

ALT  $\geq$  10 times upper limit normal

Hy's Rule, ALT  $\geq$  3 times upper limit normal and total bilirubin  $\geq$  2 times upper limit normal.

A listing of patients with ALT  $\geq$  3 times upper limit normal at any time during post-baseline will be presented. And, a listing of all laboratory values will be presented.

For the continuous laboratory analytes, change from baseline to endpoint will be assessed using an ANOVA model (see Section 6.1.2 and 6.1.3) for Study Period II, and will be summarized for Study Period III and Study Period II/III. Rank transformed data for lab analytes will be used for the laboratory analysis. Within treatment testing of change from baseline will be based on a Wilcoxon Signed-Rank Test.

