Change from baseline in vital signs (blood pressure and pulse), weight, and height data will be analyzed using an ANCOVA model with baseline values as covariates (see Sections 6.1.2 and 6.1.3). Raw values will be used for these analyses unless normality assumptions appear to be violated in which case the data will be rank transformed. These analyses will include summaries of baseline values, endpoint (LOCF) values, and change from baseline to endpoint (LOCF) by treatment group for SP II, SP III and SP II/III separately. Change from baseline in vital signs (blood pressure and pulse) and weight will also be summarized for SP IV. For SP IV, change from baseline in vital signs and weight data will be analyzed using a simple linear regression model with change from baseline as the response variable and the baseline value as the independent variable.

Change from baseline in vital signs (blood pressure and pulse) and weight will also be analyzed using an MMRM model (see Section 6.1.2) for SP II, SP III and SP II/III separately. Within treatment testing of change from baseline will be conducted.

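### Within-treatment tests of change in vital signs and weight in Study Periods III and II/III rest on baseline-adjusted LS-means whose standard errors treat the mean baseline as fixed, so their intervals are too narrow

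*SAP*

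**What the plan says.** The general rule in SAP 6.1.2 is "All tests of hypotheses will be evaluated based on a two-sided significance level of 0.05 unless otherwise specified".

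The MMRM in the same section contains pooled site, visit, baseline value and baseline-by-visit as well as treatment, and "Significance tests will be based on least-squares means (LSMean) and Type III sum-of-squares". For SP III, Section 6.1.3 says "Data presentations for Study Period III will be based on the same MMRM and ANCOVA models excluding treatment effect, where appropriate". Section 6.1.2 says much the same, but also lists ANOVA, which has no baseline covariate.

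Within-treatment tests are planned in four places:

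- **6.1.2:** "within treatment testing of change from baseline for selected safety and efficacy measures will be conducted for SP III". No test is named.
- **6.1.13.2, after Table HMGW.6.3 (efficacy):** "For continuous measures, when appropriate, within treatment testing of change from baseline will be conducted for SP III and SP II/III". No test is named.
- **6.1.14.3 (blood pressure, pulse, weight):** the MMRM of 6.1.2 is run for SP II, SP III and SP II/III separately, followed directly by "Within treatment testing of change from baseline will be conducted".
- **6.1.14.2 (laboratory):** "Within treatment testing of change from baseline will be based on a Wilcoxon Signed-Rank Test".

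The opening of Section 6.1.14, however, limits SP III safety to descriptive statistics.

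**The concern.** The models were built for the duloxetine-placebo contrast. There, adjusting for baseline gains real precision, because chance differences in baseline are removed from the comparison. Once treatment is taken out and the question becomes whether one group's mean change is zero, that gain disappears. The LS-mean is evaluated at the group's observed mean baseline, and its standard error uses only the residual variance after regression on baseline. Another sample would have a different mean baseline, and through the regression slope a different mean change. That source of error is left out. Kenward-Roger does not restore it, because baseline enters as a fixed covariate.

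Change and baseline are usually negatively correlated through regression to the mean, so the omitted term need not be small. At stake are p-values and intervals for blood pressure and pulse in adolescents over the 26-week extension and the 39-week combined period (13 + 26), where there is no control arm. A chance movement could be reported as a significant change more often than the stated 5%.

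**Working it through.** **Inputs from the SAP.** Two-sided level 0.05 (6.1.2). 184 patients randomized 1:1 with about 81% completing the acute phase (5.2), so about 92 × 0.81 = 74.5, or 75 per group. The SAP gives no SD, no baseline/follow-up correlation and no number of pooled sites, so these are assumptions below.

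**Formula.** Let X be baseline, Y follow-up, d = Y − X, ρ their correlation and k = SD(Y)/SD(X), with SD(X) = 1.

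- Slope of change on baseline: b = ρk − 1
- Residual variance: s² = k²(1 − ρ²)
- Variance the model reports for the LS-mean: s²/n
- Actual variance of the mean change: (s² + b²)/n
- Reported/actual SE: R = √[s²/(s² + b²)], which is √[(1 + ρ)/2] when k = 1
- Actual level of a nominal 5% test: 2[1 − Φ(1.96R)]

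n cancels in R, so a larger extension sample does not help.

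**Reference: the plan's 5%.** A paired t-test on simulated data of this kind (n = 75, k = 1, no true change) rejects 4.5% to 5.1% of the time, so the nominal level is attainable.

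**Baseline as the only covariate, k = 1.** Worked case ρ = 0.5: b = −0.5, s² = 0.75, s² + b² = 1.00, R = √0.75 = 0.866, level = 2[1 − Φ(1.697)] = 9.0%.

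| ρ | R | Level, formula | Level, simulated ANCOVA |
|---|---|---|---|
| 0.3 | 0.806 | 11.4% | 11.3% |
| 0.5 | 0.866 | 9.0% | 9.0% |
| 0.7 | 0.922 | 7.1% | 7.0% |

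A simulated unstructured three-visit model with baseline-by-visit on complete data agrees: 10.8%, 9.2% and 7.2%.

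**With pooled site, as the SAP specifies, k = 1.** LS-means weighting sites equally:

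| ρ | 30 sites assumed | 15 sites assumed |
|---|---|---|
| 0.3 | 9.5% | 9.7% |
| 0.5 | 7.2% | 7.4% |
| 0.7 | 6.2% | 5.8% |

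This gives about 6% to 10%.

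**Sensitivity to the SD ratio (formula, baseline only).**

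| k | ρ = 0.3 | ρ = 0.5 | ρ = 0.7 |
|---|---|---|---|
| 0.8 | 16.5% | 13.8% | 12.0% |
| 1.25 | 8.3% | 6.4% | 5.2% |
| 1.5 | 6.7% | 5.4% | 5.0% |

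**High correlation.** At k = 1 and ρ = 0.9 the level is 5.6%, and it tends to 5% as ρ approaches 1. That is the likely position for weight. It does rely on similar SDs: at ρ = 0.9 the formula gives 12.6% for k = 0.8 and 8.4% for k = 1.5.

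**After correction.** Adding b²/n to the variance in the repeated-measures simulation gives 4.4% to 5.0%.

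**The case against.** The strongest case against is about scope and importance.

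- **The link from model to test is mostly inferred.** It is explicit only for vital signs and weight. For efficacy, Sections 6.1.2 and 6.1.13.2 name no test, ANOVA without baseline is allowed, and the models are offered for presenting data where appropriate. A paired test would contradict neither section. This stands. A reader might infer that all extension-phase efficacy tests are affected, but the SAP does not say so.
- **The size is unknown.** Without SDs or correlations, any figure is conditional. A reader might take about 11% as the plan's error rate, but that needs ρ = 0.3, equal SDs and a model without site, whereas the SAP's model includes site. For pain in SP II/III, the entry requirement of at least 4 on BPI average pain (Table HMGW.6.2) probably narrows the baseline SD, giving k above 1 and less inflation. This also stands.
- **There is other SP III inference.** A reader might think the within-group test is the only one. Section 6.1.13.2 also sets a maintenance test in acute-phase responders, with a one-sided 97.5% bound against a 1.5-point margin. It uses t-statistics and states no covariate adjustment.
- **Conditioning on baseline is common, and these analyses are secondary and uncontrolled.** That lowers the priority. It does not make the standard error right for the mean change in the population, and at none of the SD ratios and correlations computed here did the formula give a level below 5%.

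**Conclusion.** The point holds for blood pressure, pulse and weight in SP III and SP II/III. As written, the plan gives within-treatment intervals that are too narrow whenever change depends on baseline. Under the assumptions shown (about 75 per group, equal SDs, correlation 0.3 to 0.7, pooled site in the model), a nominal 5% test runs at about 6% to 10%. Across SD ratios from 1.5 to 0.8 the range is roughly 5% to 16%. The effect is negligible where correlation is near 1 and SDs are similar, as is likely for weight. Efficacy measures are affected only if the models of 6.1.2 and 6.1.3 supply their unnamed tests.

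A reader might extend this to the primary result. The documents do not support that: the SP II arm contrasts keep a valid gain from baseline adjustment. The signed-rank laboratory tests and, as far as stated, the maintenance t-test are also outside the point. Priority is minor.

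**What to change.** In 6.1.2, 6.1.3 and 6.1.14.3, state that within-treatment tests and intervals in SP III and SP II/III do not condition on baseline, and name the method:

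- At the LOCF endpoint, a paired t-test, or the signed-rank test where the data are non-normal (as already used for laboratory values).
- For repeated measures, place baseline in the response vector and test the visit-minus-baseline contrast, or use a standard error that includes the variance of the mean baseline.

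Name the test for efficacy measures in 6.1.13.2 as well, and keep the baseline-adjusted models for SP II contrasts. Reconcile 6.1.14.3 with the opening of 6.1.14, which makes SP III safety descriptive only.

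The cost is a few sentences and a small program change. Intervals will widen. Under equal SDs with baseline as the only covariate, the increase is about 8% at ρ = 0.7 (1/0.922 = 1.085) to 24% at ρ = 0.3 (1/0.806 = 1.241).

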#### **6.1.4. Handling of Dropouts or Missing Data**

Missing efficacy and safety data can occur for multiple reasons, including missed patient visits (for example, patients discontinuing from the study early) and scales or measures with missing item scores.

When change from baseline is assessed, only patients with a baseline and at least one post-baseline measurement will be included in the analyses.

For the repeated measures analyses, the model parameters are simultaneously estimated using restricted likelihood estimation incorporating all of the observed data.

Unless otherwise specified, when a total score or an average score is calculated from individual items, it will be considered missing if any of the individual items are missing.

For the assessment of efficacy, handling of missing data depends on the missing data mechanism assumptions. There are three missing data mechanisms: 1) missing completely at random (MCAR), 2) missing at random (MAR) and 3) missing not at random (MNAR). Three primary statistical approaches to handling missing data will be utilized: mixed model repeated measures (MMRM) analyses, ANCOVA/ANOVA using last observation carried forward (LOCF) change from baseline to endpoint, and ANCOVA/ANOVA using baseline observation carried forward (BOCF) change from baseline to endpoint. The LOCF and BOCF imputation methods in general make MNAR assumption, while the repeated measures analysis assumes MAR. A sensitivity analysis will be performed to assess the impact of missing data assumptions on the primary analysis conclusions (see section 6.1.13.3 for details).

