The same MMRM, ANOVA and ANCOVA models excluding treatment effect will be used to present data for Study Period III, where appropriate.

Unless otherwise specified, for all analyses using the last-observation-carried forward (LOCF) approach in Study Period II, endpoint is defined as the last nonmissing observation obtained from Visit 3 through Visit 8; for the analyses using LOCF in Study Period III, endpoint is defined as the last nonmissing observation from Visit 9 through Visit 15.

In the analyses of some efficacy variables for Study Period II, the baseline-observation-carried-forward (BOCF) approach is considered. The BOCF endpoint is defined as follows:

For randomized patients who complete the treatment period (that is, complete the scheduled Visit 8) and have last nonmissing value at Visit 8, the BOCF endpoint is defined as the last nonmissing observation, for randomized patients who discontinue early (that is, do not complete the scheduled Visit 8) but with at least one non-missing baseline value, the BOCF endpoint is defined as the baseline value.

Categorical comparisons between treatment groups will be performed using Cochran-Mantel-Haenszel (CMH) test controlling for pooled investigative site and Fisher's exact test for Study Period II, when appropriate. For the categorical data, the number and percentage of patients for the categorical variables will be presented for Study Period III.

Where appropriate, variables will be summarized descriptively (frequency and percent will be summarized for categorical variables; number of patients with a non-missing observation, mean, SD, median, minimum, and maximum will be summarized for continuous variables) by study visit.

For those data summaries accompanied by individual patient data listings, data will be sorted by investigator ID, patient ID, and visit or event number if it is available.

Changes made to the data analysis methods will not necessarily require a protocol amendment and will be described in an updated SAP and reflected in the final report.

Statistical analysis of this study will be the responsibility of Eli Lilly and Company or designee. SAS® software will be used to perform most or all statistical analyses.

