**Table HMGW.6.3 Secondary Efficacy Analysis**

Efficacy Variable	Derivation and Details	Analysis
1. Area under the curve of pain relief (AUC) a. BPI average pain severity	The relief score at a visit is defined as baseline score minus the BPI average pain score at the particular visit. The	Variable 1.a will be analyzed by the ANCOVA model described in Section

	area under the curve of relief (AUC) is the sum of each trapezoidal area circumscribed by the sides of relief scores at two consecutive non-missing visits and the side of days between the two visits.	6.1.2 and 6.1.3 (using baseline BPI average pain severity as covariate) for Study Period II.
2. Change from baseline to LOCF endpoint: a. BPI pain severity items: worst pain, least pain, average pain, and pain right now b. BPI-Interference items: general activity, mood, walking normally, normal work, relations with others, sleep, enjoyment of life, and school work (new item). c. BPI Average Interference score d. PPQ average pain, pain right now, and worst pain rating e. CGI-S: Mental Illness f. CGI-S: Overall Illness g. FDI-child h. FDI-parent i. CDI: total score j. MASC: total score, factor scores	a-b. eCRF data. c. Average of the non-missing ratings of the 8 individual items. d-f. eCRF data. g-h. FDI total score is the sum of 15 individual item scores. i. CDI total score is the sum of 27 individual item scores. j. MASC total score is the sum of 39 individual item scores ; the 4 factor scores are 1) physical symptoms, 2) social anxiety, 3) harm avoidance and 4) separation anxiety	The Variable 2.a to 2.j will be analyzed by the ANCOVA models as described in Section 6.1.2 and 6.1.3 for Study Period II.
3. Change from baseline to BOCF endpoint: a. BPI average pain severity b. PPQ average pain rating	a-b. eCRF data.	The Variable 3.a to 3.b will be analyzed by the ANCOVA models as described in Section 6.1.2 and 6.1.3 for Study Period II.

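### One blank item sets an FDI, CDI or MASC total to missing, an avoidable loss of precision in secondary measures that prorating nearly complete scales would remove

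*SAP*

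**What the plan says.** Section 6.1.4 sets a default. "Unless otherwise specified, when a total score or an average score is calculated from individual items", the score is lost if one item is blank: "it will be considered missing if any of the individual items are missing". The same section limits change-from-baseline analyses: "only patients with a baseline and at least one post-baseline measurement will be included in the analyses".

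Table HMGW.6.3 defines the long scales as plain sums and adds no rule for blanks:
- FDI, child and parent versions: "FDI total score is the sum of 15 individual item scores".
- CDI: "CDI total score is the sum of 27 individual item scores".
- MASC: "MASC total score is the sum of 39 individual item scores", plus four factor scores.

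For BPI Average Interference the table does give its own rule: "Average of the non-missing ratings of the 8 individual items". No minimum number of answered items is stated.

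In Study Period II, FDI, CDI and MASC appear only as change to LOCF endpoint, analysed by ANCOVA (variables 2.g to 2.j). They are in neither the BOCF list (3.a and 3.b) nor the repeated-measures list (4.a to 4.e). Section 6.1.2 defines the LOCF rule for that period: "endpoint is defined as the last nonmissing observation obtained from Visit 3 through Visit 8". Section 6.1.15 uses the baseline median CDI score to form a subgroup for the suicidality analyses.

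**The concern.** The default is mild for a short scale and costly for a long one. A patient who answers 38 of 39 MASC items at Week 13 is handled as though the questionnaire had not been completed. What follows depends on what else was collected. If an earlier complete total exists, LOCF uses it in place of the Week 13 value. If none exists, the patient drops out of the comparison. A blank at baseline can also exclude a patient, unless another complete baseline total is available. For CDI, a blank baseline item can leave the patient on neither side of the median split.

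FDI-child, FDI-parent, CDI and MASC are all named in the secondary objectives (Section 4.2). As LOCF ANCOVA is their only planned treatment comparison in Study Period II, no second analysis of the same totals makes up for the lost data. At stake is information that was collected and is then not used.

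**Working it through.** **Inputs from the SAP.** Items per scale: FDI 15, CDI 27, MASC 39 (Table HMGW.6.3). Planned randomization is about 184 with about 81% completing Week 13 (Section 5.2), so 184 × 0.81 = about 149 completers.

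**Input that is assumed.** The SAP gives no item blank rate, so there is no planned figure to reproduce. I take p = 0.1%, 0.5% and 1% per item, with blanks independent across items.

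**Step 1: chance that a total is lost at one visit.** P(lost) = 1 − (1 − p)^k for k items. Example, MASC at 0.5%: 1 − 0.995^39 = 1 − 0.8224 = 17.8%.

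| Scale | k | p = 0.1% | p = 0.5% | p = 1% |
|---|---|---|---|---|
| MASC | 39 | 3.8% | 17.8% | 32.4% |
| CDI | 27 | 2.7% | 12.7% | 23.8% |
| FDI | 15 | 1.5% | 7.2% | 14.0% |

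If blanks cluster in a few patients, the same average rate loses fewer totals.

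**Step 2: Week 13 totals lost among 149 completers** (149 × P(lost)).
- MASC: about 5.7, 26.5 and 48.3.
- CDI: about 4.0, 18.9 and 35.4.
- FDI: about 2.2, 10.8 and 20.9.

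**Step 3: effect on the standard error if those patients leave the analysis.** The approximate inflation is 1/√(1 − P(lost)).
- At 0.5%: MASC 1/√0.8224 = 1.10; CDI 1/√0.8734 = 1.07; FDI 1/√0.9276 = 1.04.
- At 0.1%: MASC 1/√0.9617 = 1.02.
- At 1%: MASC 1/√0.6757 = 1.22.

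Where an earlier total is carried forward, the patient stays in and the cost is an older value instead.

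**Step 4: the same totals under proration with at least 80% answered.** 0.8 × 39 = 31.2, so 32 MASC items are needed and 7 may be blank. 0.8 × 27 = 21.6, so 22 CDI items are needed and 5 may be blank. 0.8 × 15 = 12, so 3 FDI items may be blank. The binomial chance of exceeding these limits at p = 1% is 4.7 × 10⁻⁹ (MASC), 2.5 × 10⁻⁷ (CDI) and 1.2 × 10⁻⁵ (FDI). A stricter limit of 10% blank (3, 2 and 1 items) still cuts the loss at 1% to 0.06%, 0.24% and 0.96%.

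**Step 5: BPI Average Interference.** The chance that 5 or more of the 8 items are blank, even at p = 2%, is 1.7 × 10⁻⁷. A floor of 4 answered items would change almost no score.

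**The case against.** The strongest reply is that the rule is clear, reproducible and conservative, and that preferring proration is a matter of choice. That is right as far as it goes: the SAP makes no error here and leaves nothing ambiguous. The size also rests on a blank rate that the document does not supply. At 0.1% the loss is only 1.5% to 3.8%, and the 0.5% case widens standard errors by about 4% to 10%. The affected measures are a few among many secondary variables. A single proration rule could also conflict with an instrument's own scoring rule, which is why the fix puts that rule first.

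Four stronger readings are tempting, and the document supports none of them.
- A reader might see a contradiction between the all-items rule and the BPI interference average. The opening condition of the default expressly allows a scale-specific rule.
- A reader might infer that endpoints are pulled back to earlier, less treated time. That needs an earlier collection of these scales. The SAP does not show their visit schedule, and Section 6.1.2 notes that some variables are not collected at every visit.
- A reader might infer a biased treatment comparison. Nothing indicates that blanks would differ by arm.
- A reader might treat an interference average resting on one item as a practical threat. The wording permits it, but Step 5 shows that it would be extremely rare under independent blanks.

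What stands is that nearly complete questionnaires are discarded for no stated benefit, when a cheap alternative would keep them.

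**Conclusion.** The point holds as an inexpensive improvement to the plan. The all-items default, applied to scales of 15, 27 and 39 items with LOCF ANCOVA as the only Study Period II comparison, gives up precision that could be kept. The loss may be trivial or substantial, from a few percent of totals at a 0.1% blank rate to about a third of MASC totals at 1%. These figures assume independent blanks at rates that the SAP does not give, and clustering would reduce them. The primary endpoint is a single BPI rating and is unaffected. For the CDI median split, the consequence is at most an unclassified patient, and only where no other complete baseline total from Visits 1 to 2 is available.

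**What to change.** In Section 6.1.4, add a rule for the FDI total (child and parent), the CDI total, the MASC total and each MASC factor:
1. Where the instrument has its own missing-item rule, cite it and use it.
2. Otherwise, if at least 80% of the items are answered, score the total as the mean of the answered items times the number of items.
3. Below 80%, set the score to missing.

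Apply the same rule at baseline, so that it also governs the CDI median split in Section 6.1.15. The 80% threshold is a reasonable convention and does not come from the document; Step 4 shows that a stricter limit works nearly as well. A minimum number of answered items for BPI Average Interference is optional.

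The cost is a short SAP paragraph and a few derivation lines, best fixed before treatment codes are opened. The downside is a slight error from standing in the patient's own item mean for a blank. Reporting how many totals were prorated, by arm and visit, would let readers judge it.
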